According to the Section 5 - Neuro-Ophthalmology in the *Basic and Clinical Science Course* textbooks, the workup for anisocoria, or unequal pupil size, is to be done according to a flow-sheet^{appx.1}. For anisocoria that is greater in bright light than dim light, a low-dose pilocarpine test is indicated to determine if the anisocoria is due to either Adie's tonic pupil or pharmacological dilation versus third cranial nerve palsy. If the pupil constricts to low-dose pilocarpine, the patient is determined to have Adie's tonic pupil, or parasympathetic denervation. However, if the pupil does not constrict with low-dose pilocarpine, a high-dose pilocarpine test is the next step in the work-up. If the pupil constricts to high-dose pilocarpine, the patient is determined to have a third cranial nerve palsy which then needs to be further evaluated with imaging including CT angiogram due to concern for aneurysm rupture. However, if the pupil does not constrict to high-dose pilocarpine, the patient likely has anisocoria due to pharmacological dilation. Suspected iatrogenic anisocoria does not require further evaluation with imaging as it should resolve as the pharmacological substance causing the dilation is metabolized. The flow chart in the *BCSC* books does not consider a phenomenon that may occur as the pharmacological substance causing dilation wears off. We propose that there is a period of time in which a pharmacologically dilated pupil may constrict to high-dose pilocarpine, but still appear dilated, and thus anisocoric. In this case, the patient would require additional imaging with CT angiogram, even though their history may not support any findings concerning for third nerve palsy due to aneurysm. Depending on the patient's history, conducting further imaging may have greater risks and financial burden that are unlikely to provide valuable information. If a patient has history of possible pharmacological dilation in absence of aneurysm symptoms including headache, nausea, vision changes, loss of consciousness, then the patient should not be further evaluated with imaging. We aim to demonstrate the period in which a pharmacologically dilated eye may appear anisocoric on exam, but still respond to 1% pilocarpine.

B. BACKGROUND AND SIGNIFICANCE

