After screening, participants will be asked to return to the clinic on a scheduled day (within a week of screening) to have their left eye dilated. At this visit, the diameter of their left pupil will be measured using a Near card in a windowless room with a set light-level. Tropicamide will be our agent of choice for pharmacological dilation. Tropicamide is widely used in ophthalmology clinics to dilate the pupil of the eye and has a suspected effect time of 4-8 hours of dilation.⁵ Participants will receive one drop of tropicamide in the left eye and, after the drops have had time to take effect, about 20-30 minutes, the diameter of the participant's pupil will be measured again. After measurement of baseline pupillary response to tropicamide, participants will be dismissed and asked to return to the clinic in 3-4 hours. At this time, we will record the diameter of the left pupil again and compare it to the participant's baseline as well as post-dilation diameter. One drop of 1% pilocarpine will then be administered to the participant's left eye. Pilocarpine 1% is a miotic agent that is the current standard for workup of anisocoria of unknown cause according to the 2021-2022 Basic and Clinical Science Course^{appx.1}. After the pilocarpine has been given 10-15 minutes to take effect,

any change in pupillary diameter will be measured. Following this measurement, participants will be dismissed. A positive result will be indicated by a constricting response of the pupil after administration of pilocarpine of > 1mm in diameter, while still appearing anisocoric on exam (clinically significant difference in pupillary diameter between right and left eyes). Application of dilating and constricting eye drops, as well as measurement of pupillary response will be performed by medical student volunteers. These volunteers will receive training on sterile eye-drop application technique as well as pupillary measurement using a Near card.

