In the event that no response to 1% pilocarpine is observed at the initial post-dilation visit, or if pupillary diameter has returned to baseline prior to the administration of 1% pilocarpine at any point, we will ask this participant to return to the clinic on another day to have the process repeated in their right eye, with the modification of either shortening or lengthening the interval of reassessment based on their left eye's response to the drops. This is to avoid any confounding from the administration of subsequent pilocarpine eye drops in the same eye. If the left pupil returned to baseline pupillary diameter prior to the 3-4 hour reassessment, we will have them return 2-3 hours following dilation of their right eye to have their pupillary diameter checked and the administration of Pilocarpine 1% repeated. If the left pupil remained dilated with no response to 1% pilocarpine at 3-4 hours, we will have them return 4-5 hours following dilation of their right eye to have their pupillary diameter checked and the administration of Pilocarpine 1% repeated. Repeating the protocol with varied assessment times in the contralateral eye will be in an effort to compensate for expected variation in each participant's response to tropicamide and 1% pilocarpine. Despite this, it is possible that we will not be able to capture this critical window in each participant, if one exists. However, we do not believe it will be necessary to demonstrate the phenomenon in all participants, and a minimum of 2 positive results should be sufficient to demonstrate our proposed concept for this preliminary study.

E. PROTECTION OF HUMAN SUBJECTS

1. TARGET POPULATION:

We plan to conduct the study with 15 medical student volunteers at the University of South Carolina Greenville. Exclusion criteria include a history of angle closure glaucoma, any other type of glaucoma, or any elevated eye pressure readings as well as any history of intraocular surgery or procedure. Exclusion will also occur if the participant is found to be hyperopic to >+1 diopter, has an intraocular pressure of > 22 mm Hg in either eye, or displays an iridocorneal angle where trabecular meshwork cannot be seen for greater than half of the angle in either eye, as these features are known to increase the risk of angle closure glaucoma when using dilating eye drops.

Finally, those with a known allergy to natural rubber latex will be excluded from the study.

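### A positive result requires a right-left pupil difference, but no step schedules or records the fellow pupil, and the bright-light condition in the conclusion cannot be shown at the single light level described

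*Protocol*

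**What the plan says.** Section D gives a positive result two parts. The first is within the eye: constriction of more than 1 mm after 1% pilocarpine. The second is between the eyes: "while still appearing anisocoric on exam (clinically significant difference in pupillary diameter between right and left eyes".

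Four readings are described for the left-eye test:

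- At baseline, "the diameter of their left pupil will be measured using a Near card in a windowless room with a set light-level".
- About 20 to 30 minutes after tropicamide, the participant's pupil (singular) is measured again.
- At 3 to 4 hours, before pilocarpine, "we will record the diameter of the left pupil again and compare it to the participant's baseline" and also with the post-dilation diameter.
- At 10 to 15 minutes after pilocarpine, "any change in pupillary diameter will be measured". No eye is named.

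The right-eye repeat is triggered by no response to pilocarpine, or "if pupillary diameter has returned to baseline prior to the administration of 1% pilocarpine at any point". It again describes checking the diameter after dilation of the right eye, with no reading of the left.

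The opening section states the aim as showing the period in which "a pharmacologically dilated eye may appear anisocoric on exam, but still respond to 1% pilocarpine". It introduces the work-up with the words "For anisocoria that is greater in bright light than dim light".

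Section E.1 says the study will serve as a pilot if, in two or more participants, the pupil constricts by more than 1 mm and keeps the appearance of an anisocoria that is worse in bright light. Section D likewise treats two positive results as sufficient.

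**The concern.** The study sets out to show that a pupil visibly larger than its fellow can still constrict to 1% pilocarpine, and so be sent for imaging under the current algorithm. The between-eye part of the definition carries that message. Constriction alone does not.

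Followed as written, the protocol yields a number in mm for constriction but no recorded number for the right-left difference, and nothing that compares bright with dim light. An analysis plan could later set a threshold or name the deciding reading. It could not recover fellow-eye or second-light-level readings that were never taken.

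The deciding reading matters as well. If anisocoria is judged after pilocarpine, an eye that constricts by more than 1 mm down to its fellow's size is negative. Section D then offers it no repeat, because it did respond and was not at baseline beforehand. If anisocoria is judged before the drop, the same eye is positive.

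**Working it through.** The plan gives no figure on this point to reproduce. The check sets the definition against the readings and then works through what the open choices change. All diameters below are assumed for illustration, because the protocol gives none.

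**1. Readings against the definition.** Write T for the treated pupil and F for the fellow pupil.

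| What must be shown | Readings needed | Explicitly scheduled |
|---|---|---|
| Constriction > 1 mm | T before and after pilocarpine | Both |
| Right-left difference | T and F at the deciding reading | T only |
| Anisocoria greater in bright light | T and F, each in bright and in dim light (4) | T at one set level (1 of 4) |

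In a right-eye repeat the fellow is the left eye. Its recorded values come from another day, so they are not a concurrent comparison.

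**2. What the own-baseline comparison assumes.** With subscript 0 for baseline and 1 for the later reading:

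T1 − F1 = (T1 − T0) + (T0 − F0) − (F1 − F0)

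The protocol's comparison supplies only T1 − T0. It equals the right-left difference if T0 = F0 (equal pupils at baseline) and F1 = F0 (fellow unchanged), or if the two departures happen to cancel. No scheduled reading checks either condition.

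Example: T0 = 4.0 mm and T1 = 4.5 mm.

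- Against own baseline: 4.5 − 4.0 = +0.5 mm.
- Against a fellow pupil of 3.5, 4.0 or 4.5 mm: +1.0, +0.5 or 0 mm.

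The same recorded data fit anything from a 1 mm anisocoria to none.

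**3. Which reading decides.**

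- Towards after pilocarpine: Section D's statement that the eye constricts while still appearing anisocoric; the opening section's proposal that "a pharmacologically dilated pupil may constrict to high-dose pilocarpine, but still appear dilated, and thus anisocoric"; and Section E.1's wording that the appearance is maintained.
- Allowing before pilocarpine: the aim sentence, "a pharmacologically dilated eye may appear anisocoric on exam, but still respond to 1% pilocarpine". The retest trigger, "if pupillary diameter has returned to baseline prior to the administration of 1% pilocarpine at any point", is weak evidence, since an eye already at baseline is uninformative under either rule.

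Let c be the threshold in mm.

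- Pre-drop rule: T(pre) − F ≥ c.
- Post-drop rule: T(post) − F ≥ c. With T(pre) − T(post) > 1 and the same F at both readings, this implies T(pre) − F > 1 + c.

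For c = 0.5 mm, the difference needed before the drop is ≥ 0.5 under the first rule and > 1.5 under the second. For c = 1.0 mm it is ≥ 1.0 and > 2.0.

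Examples with F = 4.0 mm; both eyes constrict by 1.5 mm:

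| Treated pupil, pre to post | Difference before | Difference after | Pre-drop rule | Post-drop rule |
|---|---|---|---|---|
| 5.5 to 4.0 mm | +1.5 | 0 | Positive at c = 0.5 and 1.0 | Negative at both |
| 6.0 to 4.5 mm | +2.0 | +0.5 | Positive at both | Positive at c = 0.5, negative at 1.0 |

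**The case against.** Several points on the other side have weight.

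- *Both eyes will be looked at.* This stands. Anisocoria judged on examination implies at least a look at both pupils, and the post-pilocarpine reading names no eye. A reader might infer that the fellow eye is never examined; the text does not support that. The gap is that no fellow-eye diameter is explicitly scheduled or recorded, so the judgement could not be checked afterwards. The appendices are not shown, but none is cited as a pupil-measurement form.
- *The deciding reading is given.* This stands in part. A reader might infer that the time point is wholly unstated. In fact most of the wording leans towards after pilocarpine, and only the aim sentence really allows an earlier reading. It is ambiguous, not absent.
- *The threshold and time point belong in an analysis plan.* On their own they could be left there, and a plan may exist unseen. That does not help with readings not taken.
- *The bright-light phrase may only name the work-up category.* This is possible, since the opening section uses it that way and Section D omits it. But Section E.1 places it inside the condition for calling the study a successful pilot, so the two definitions differ as written.
- *It is a small preliminary study.* True, and success is claimed only as grounds for further research. With two positives enough, however, each classification counts.

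**Conclusion.** The point holds as a gap between definition and measurement, and it should be fixed before the first participant is tested. The between-eye half of the endpoint has no explicitly scheduled fellow-eye reading, and the bright-light condition in Section E.1 cannot be shown from one light level. Both follow from the text alone. The ambiguity of the deciding reading and the missing mm threshold are secondary. They matter because they change who is positive: judging after the drop raises the difference required before it from at least c to more than 1 + c mm.

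The mm examples rest on assumed diameters and on thresholds of 0.5 and 1.0 mm that are not in the protocol. They show that the classification can flip, not how often it will.

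A reader might go further and infer that miscalled eyes would produce a false success. The documents give no rate of miscalls or of true positives, so that cannot be quantified. The direction of anisocoria is not in dispute: the treated pupil is meant to be the larger.

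**What to change.** In Section D:

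1. Measure and record both pupils with the Near card under the set light level, at least at baseline, before pilocarpine and after pilocarpine. Do this in the left-eye test and in any right-eye repeat.
2. State whether the pre- or post-pilocarpine reading decides anisocoria. Define anisocoria as the treated pupil exceeding the fellow by at least a threshold in mm, set by the investigators beforehand.
3. Use one definition of a positive result in Sections D and E.1. Either drop the bright-light condition, or add a bright and a dim reading of both pupils at the deciding time point.

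Strictly, the definition needs only one fellow-eye reading, at the deciding time. The baseline reading is worth adding because it shows whether the pupils were equal to begin with.

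Cost: 3 extra readings per tested eye, so 3 × 15 = 45 for 15 tested eyes and at most 3 × 30 = 90 if all 15 participants repeat in the right eye. Keeping the bright-light condition adds 2 more per tested eye if the set level serves as one of the two levels, or 4 if it does not. Dropping it costs only wording. No visit, drug or participant is added. The downside is that a fixed threshold may turn some eyes that look anisocoric into negatives.

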[name] is a fourth-year medical student who is currently in good standing to graduate from the University of South Carolina School of Medicine Greenville in 2022. He has completed CITI training through the University of South Carolina to conduct human subjects research.

D. RESEARCH DESIGN AND METHODS AND DATA ANALYSIS

Recruitment of participants for this study will be done at the University of South Carolina School of Medicine Greenville. We will be recruiting 15 otherwise healthy participants with no significant ophthalmological history. Data collection will be done at the Prisma Health Eye Institute - Greenville. Data analysis will be performed by [name] at Prisma Health.

After participants are recruited, they will be brought into the ophthalmology clinic where they will first be consented for the study by a physician^{appx.5}. Following consent, participants will complete paperwork such as demographics^{appx.2}, contact information^{appx.3} and exclusion/inclusion criteria forms^{appx.4}. They will then be screened for hyperopia using a phoropter, have their intraocular pressures measured using a Reichert Tono-Pen Avia , and have their iridocorneal angle measured with a gono lens. The purpose of this exam is to screen out participants with hyperopia > +1 diopter, iridocorneal angles where trabecular meshwork cannot be seen for greater than half of the angle, and/or intraocular pressures of > 22 mm Hg, as these conditions may increase the risk for mydriatic agent-induced angle closure glaucoma^{appx.4}. An additional ophthalmic medication, proparacaine hydrochloride 0.5%, will be used to numb the eyes before measuring intraocular pressures and prior to gono lens examination. This medication is commonly used as an ocular surface analgesic during routine eye examinations. This screening exam will take place at least one day prior to administration of any dilating drops, as examination of the angle with gono lens may affect pupillary dilation through corneal contact. The initial exam will be performed by a physician licensed to practice ophthalmology.

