We chose a sample size of 15, as this is a proof of concept, and thus we would like to demonstrate a minimum of 2 instances of pharmacologically dilated eyes that constrict $> 1\text{mm}$ to 1% pilocarpine. We feel that at least 15 participants will be necessary to guarantee that we witness at least 2 instances of the proposed phenomenon, assuming that we test both of their eyes independently with varying timeframes of reassessment. If we limited the study to < 15 , we may not be able to witness the desired effect without subjecting participants to multiple rounds of testing.

If we are able to describe a period in which the pharmacologically dilated pupil responds to 1% pilocarpine with $>1\text{mm}$ of constriction but maintains the appearance of anisocoria that is worse in bright light in two or more participants, this study will serve as a pilot study to demonstrate the need for further research on the concept in order to make an addendum to the current treatment algorithm for anisocoria.

2. RECRUITMENT PLANS:

Recruitment of subjects will be done in person at the University of South Carolina School of Medicine Greenville, via the school newsletter that is sent to the student body on a weekly basis, and with email correspondence via the Ophthalmology interest group at the school. Approval has been obtained from school administration to conduct recruitment onsite and via electronic correspondence^{appx.6,7}.

3. EXISTING DATA/SAMPLES:

There are not any existing data or samples for this study.

4. CONSENT/ASSENT:

The participants will be asked to sign a consent form prior to participation^{appx.5}. The study doctor will consent the participants before any study procedures are completed. All communication will take place in a private setting. The participant will be given ample time to read the consent and have all questions answered prior to providing signature. The consent will be signed and dated by all parties and a copy will be provided to the participants at the time of consent. The consent will discuss risks of eye dilation including blurred vision for several hours following drop administration. Participants will also be informed of the risk of angle-closure glaucoma, and will be screened for any significant ophthalmological history, which will exclude them from the study. Participants will have ample opportunity to ask any questions concerning what to expect from and potential risks of dilating drops.

5. POTENTIAL RISKS:

Drug Tropicamide:

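### The anisocoria half of a positive result ignores any pupil difference present before dosing, and neither the stated eligibility criteria nor the baseline measurements would detect one

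*Protocol*

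**What the plan says.** **Definition of a positive result (protocol, section D).** Two conditions apply. The pupil must constrict by more than 1 mm after pilocarpine, "while still appearing anisocoric on exam (clinically significant difference in pupillary diameter between right and left eyes"). No millimetre cut-off, direction or baseline correction is attached to the second condition.

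**Eligibility (section E.1).** "Exclusion criteria include a history of angle closure glaucoma, any other type of glaucoma, or any elevated eye pressure readings as well as any history"; the sentence ends with operations or procedures inside the eye. Hyperopia, raised pressure and a narrow angle follow, "as these features are known to increase the risk of angle closure glaucoma when using dilating eye drops". The list closes with latex: "Finally, those with a known allergy to natural rubber latex will be excluded from the study". More generally, section D says "We will be recruiting 15 otherwise healthy participants with no significant ophthalmological history", and section E.4 says that participants "will be screened for any significant ophthalmological history, which will exclude them from the study".

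**Screening examination (section D).** "The purpose of this exam is to screen out participants with hyperopia > +1 diopter, iridocorneal angles where trabecular meshwork cannot be seen" for more than half of the angle, or raised pressure. Pupil size and symmetry are not mentioned.

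**Baseline at the dilation visit (section D).** "the diameter of their left pupil will be measured using a Near card in a windowless room with a set light-level". At 3-4 hours the left pupil is compared with its own earlier values. No right-eye reading before the drops is described.

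**Success bar (sections D and E.1).** Two positive results among 15 participants are taken as enough to demonstrate the concept.

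**The concern.** The opening section proposes that a pupil whose pharmacological dilation is wearing off can respond to 1% pilocarpine and yet still look dilated, so that the eyes are unequal. A right-left difference stands for residual drug dilation only if the pupils were equal at the start. The protocol neither requires that nor records it.

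A healthy student with a harmless, unnoticed inequality has no ophthalmological history to report and passes an examination of refraction, pressure and angle. If that participant is later scored as anisocoric, part or all of the difference may have nothing to do with tropicamide. Because the right pupil has no baseline, the analysis cannot separate the pre-existing part from the drug part. With a bar of two positives and no control group, one or two misattributed cases could settle the study's only claim.

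**Working it through.** **Is there a plan figure to reproduce?** No. The protocol gives 15 participants and a bar of 2 positives, without an assumed response rate, so no calculation lies behind them.

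**Step 1: what the rule scores.** Let L0 and R0 be the pupils before any drop, L1 the left pupil at reassessment before pilocarpine, and L2 the left pupil afterwards. Assume that the untreated right pupil stays at R0 under the set light level. The rule is:

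- condition 1: L1 − L2 > 1 mm;
- condition 2: the difference between L2 and R0 is judged clinically significant.

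Since L2 − R0 = (L0 − R0) + (L2 − L0), condition 2 adds the pre-existing difference to what is left of the drug effects. Only the second term bears on the hypothesis.

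**Step 2: illustrative diameters (chosen for this check, not from the protocol).**

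| Case | R0 | L0 | L1 | L2 | L1 − L2 | L2 − R0 | L2 − L0 |
|---|---|---|---|---|---|---|---|
| Treated pupil naturally larger | 4.0 | 5.0 | 6.0 | 4.8 | 1.2 | 0.8 | −0.2 |
| Untreated pupil naturally larger | 5.0 | 4.0 | 5.2 | 4.0 | 1.2 | −1.0 | 0.0 |
| Equal pupils | 4.5 | 4.5 | 6.0 | 4.5 | 1.5 | 0.0 | 0.0 |

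In the first case the eye ends 0.2 mm below its own baseline, so it is no longer dilated, yet it is positive if 0.8 mm counts as clinically significant. The second case can also count, because the rule has no direction. The third, with equal pupils and a full return to baseline, is correctly not positive.

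The result is similar if anisocoria is judged just before pilocarpine. With R0 = 4.0, L0 = 5.0, L1 = 5.3 and L2 = 4.2, constriction is 1.1 mm. The difference beforehand is 1.3 mm, of which only 5.3 − 5.0 = 0.3 mm comes from the drug.

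**Step 3: do other provisions catch it?**

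- The return-to-baseline rule (section D) compares the treated eye with itself, before pilocarpine. In the first case L1 − L0 = 1.0 mm, so it is not triggered.
- The exclusion for significant ophthalmological history may remove a known pupil disorder. It cannot remove an inequality nobody has noticed.
- The study-level success statement in section E.1 asks for anisocoria more marked in bright light. Section D describes measurement at one set light level, so no data are planned to apply it.

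**Step 4: size.** The documents give no prevalence, so every rate below is assumed. For n = 15, P(at least 2) = 1 − (1 − p)^15 − 15p(1 − p)^14.

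*Exposure*, with p the share of recruits who have a pre-existing inequality:

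| p | P(at least 2 of 15 enrolled) |
|---|---|
| 5% | 0.17 |
| 10% | 0.45 |
| 20% | 0.83 |

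*False positives*, with p the joint chance that a participant has the inequality, constricts by more than 1 mm and is left with a difference judged significant:

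| p | P(at least 2 false positives of 15) |
|---|---|
| 1.25% | 0.015 |
| 2.5% | 0.053 |
| 5% | 0.17 |

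For example, a 5% share combined with a one-in-four chance of meeting the remaining conditions gives 0.05 × 0.25 = 1.25%. A one-in-two chance gives 2.5%.

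**The case against.** Several points against the concern have force.

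- **The exposure figures could be misread.** A reader might infer that 0.17 to 0.83 is the chance of a spurious success. It is only the chance of enrolling at least two people with unequal pupils. A false positive also needs more than 1 mm of constriction and a large enough remaining difference. The second table in the working is the relevant one, and its lower entries are small.
- **The worked case is conditional.** A reader might infer that it is positive outright. Section D sets no millimetre cut-off, so it is positive only if 0.8 mm is judged clinically significant. Its eye was also still 1.0 mm above baseline when pilocarpine was given, so the constriction itself is a fair observation. Only the anisocoria half is contaminated.
- **The criteria may be fuller than shown.** A reader might infer that such people are certain to be admitted. Section E.1 introduces its list as what the criteria include, and the criteria form in appendix 4 is not shown. What can be said is that the body text has no such criterion and describes no symmetry check.
- **This is not purely an eligibility problem.** It lies as much in the endpoint rule, since rescoring against baseline would cure it without excluding anyone. Conversely, exclusion alone would leave the missing direction: with equal baselines, a treated pupil driven smaller than its fellow could still be called anisocoric.
- **Some of it is visible in the data.** The recorded left-eye values would show an eye that ended below its own baseline.
- **The stakes are modest.** This is a proof of concept whose success supports further research.

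These points limit the size and certainty of the problem but do not remove it. A statistical analysis plan could specify baseline-corrected scoring, but it could not recover a right-eye baseline that was never measured.

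**Conclusion.** The concern holds as a defect in the positive-result rule, combined with the lack of a symmetry check. Followed as written, the rule can count a difference that existed before any drop, and the planned baseline data cannot show how much of the observed difference that was.

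The size is unknown because the documents give no prevalence. Under assumed joint rates of 1.25% to 5% per participant, the chance that this route alone yields the two required positives runs from 0.015 to 0.17. This assumes 15 independent participants, one scored test each and a stable untreated pupil. The documents do not support the stronger inference that the study's conclusion is likely to be decided this way.

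The rule should be changed before dosing starts, because the correction is cheap and the success bar is only two positives. The sample size of 15 is unaffected.

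**What to change.** 1. In section D, measure **both** pupils with the Near card, in the same room and at the same light level, before the tropicamide drop at each dilation visit, including any repeat in the right eye.
2. State in millimetres the between-eye difference that counts as anisocoria.
3. Then do one of the following:
   - add to section E.1 an exclusion for a pre-drop right-left difference at or above that cut-off; or
   - define the second half of a positive result as the right-left difference *beyond the participant's own pre-drop difference*, reaching the cut-off in the direction of the dilated eye.

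If exclusion is chosen, the direction should still be written into the rule. With exclusion, a baseline difference below the cut-off can still contribute to the final one. Rescoring removes that contribution as well, and turns nobody away.

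The cost is one extra Near-card reading at a visit already planned and, under exclusion, possibly a few volunteers to replace.
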